The main objective of immediate implant placement is to provide an osseointegrated fixture suitable for an aesthetic and functional restoration. Bone fill in the gap between the implant and the surrounding bone is important. The buccal aspect of an implant is of great concern, especially in the esthetic zone, because the buccal bony plate is usually thin [62,63] and its resorption can result in soft tissue recession. [64]

Sohn et al. reported that sticky bone is easy to make and they are a very effective materials for the reconstruction of edentulous alveolar bone defect, based on the concept of minimally invasiveness on ridge augmentation.[27]

7. Objectives:

Primary objectives:

The primary objective of this study is to clinically assess pink esthetic score following Buccal Plate Augmentation using Sticky Bone Versus usage of sticky bone as a jumping gap filling material with simultaneous immediate implant placement in the maxillary esthetic zone.

Secondary objectives:

The secondary objectives of this study are to measure and assess :

- Crestal bone level .
- Thickness of labial plate of bone .
- Soft tissue profile /contour .
- Patient satisfaction .

Hypothesis:

Null hypothesis: there is no difference between pink esthetic score following buccal plate augmentation using sticky bone and that following sticky bone used to fill the jumping gap with simultaneous immediate implant placement in maxillary esthetic zone.

8. Trial design:

this trial is a randomized controlled clinical trial, two arms superiority trial with 1:1 Allocation.

III. Methods

A) Participants, interventions & outcomes

9. Study settings:

- The study is to be conducted in the Oral Medicine and Periodontology department, Faculty of Dentistry, Cairo University, Egypt.
- Patients are to be selected from the outpatient clinic of the department of Oral Medicine and Periodontology, Cairo University.

10. Eligibility criteria:[68]

Inclusion criteria:

- Patients aged 18 years or older.
- Presence of a non-restorable maxillary tooth in the esthetic zone including maxillary anteriors and premolars indicated for extraction.
- An intact buccal plate of bone after extraction.
- Full-mouth plaque and bleeding score not exceeding 20%.
- Patients showing motivation to comply with post-operative care instructions and follow-up appointments.

Exclusion criteria:

- Periapical infection involving the tooth to be extracted.
- Periodontal disease

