Using CBCT machine . Using the axial view, one reference line will be drawn from the apex of the implant to its platform (long axis); another line, perpendicular to the one at the long axis, will be drawn at the apex of the implant. Parallel to this, two lines will be drawn, one at 1 mm from the implant collar (R1) and another 5 mm apical to it (R2) measuring the thickness of the bone (at the buccal plate) to the nearest 0.1 mm.

Specific measurement time point: baseline and 6 months postoperatively.

4) Soft tissue profile /contour:[69]

Scanning of diagnostic casts by optical scanner.

Specific measurement time point: baseline , 3 and 6 months postoperatively.

14. Sample size:

Pink Esthetic Score (PES) was chosen as the primary outcome variable and effect size was estimated to be 1.5 based on a previous study by Abdelraheem et al (2022). Power calculation was performed at $\alpha=0.05$ and at $\beta=0.20$, equal to 80% of power. Under this assumption, at least 8 patients were needed for each group with a total number of 16 patients. This number was increased to 20 patients (10 patients in each group) to compensate for any possible dropouts.

15. Recruitment:

- Patients will be selected from the outpatient clinic of the Oral Medicine and Periodontology department, Faculty of Dentistry-Cairo University.
- Screening of patients will continue until the target sample is achieved. (Consecutive sampling)

B) Assignment of interventions

16. Allocation:

All patients who provide an informed consent for participation as well as fulfill the inclusion criteria will be included in the study.

16a. Randomization:

Patients will be randomly assigned to either test or control groups using computer generated randomization (www.randomizer.org) which will be performed by the main supervisor.

16b. Allocation concealment mechanism:

Allocation concealment will be done by creating opaque sealed envelopes. The envelope will be chosen by the patient and will only be opened after completion of extraction.

16c. Implementation

- The supervisor will generate the randomization sequence. The principal investigator will enroll the participants.

17. Masking/blinding:

- Blinding of the operator is not applicable.
- Participants, Outcome assessor (primary and secondary outcomes) & biostatistician will be blinded.

C) Data collection, management, and analysis:

18. Data collection methods

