- The phone numbers and address of the patients included in the study will be recorded or extracted from the patients' files.
- The baseline outcomes data as well those at follow-up periods will be assessed by co-supervisor.

Plans to promote participant retention and complete follow- up:

- Telephone numbers of all patients included in the study will be recorded as a part of the written consent.
- All patients will receive a phone call at the time of the pre-determined follow up.

19. Data management:

- All data will be entered and saved electronically.
- Patients' files are to be stored in numerical order and stored in a secured file. Data will be encrypted using a password.
- All data will be maintained after completion of the study.

20. Statistical methods:

Data will be analyzed using IBM SPSS advanced statistics (Statistical Package for Social Sciences), version 21 (SPSS Inc. Chicago, IL). Numerical data will be described as mean and standard deviation or median and range or interquartile range, as appropriate. Categorical data will be described as numbers and percentages. The data will be explored for normality using Kolmogrov-Smirnov test and Shapiro-Wilk test. Comparisons between two groups and over time will be done by 2-way analysis of variance for repeated measures.

If the time factor is not considerable, comparisons between the two groups for normally distributed numeric variables will be done using the Student's t-test while for non- normally distributed numeric variables will be done by Mann-Whitney test.

A p-value less than or equal to 0.05 will be considered statistically significant. All tests will be two-tailed.

D) Data monitoring:

21. Monitoring

No formal data monitoring committee will be needed since it is a study with known minimal risks.

22. Harms

Any temporary or permanent adverse effect will be recorded and documented.

No Harms are expected.

23. Audit

No formal auditing committee is available.

IV. Ethics and dissemination

24. Research ethics approval

This protocol and the template informed consent form will be reviewed by the Ethics Committee of Scientific Research -Faculty of Oral and Dental Medicine, Cairo University.

25. Protocol amendments

Any modifications to the protocol which may have an impact on the conduct of the study, potential benefit of the patient, or may affect patient safety, including changes of study objectives, study design, sample sizes, study

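### The repeated-measures ANOVA in section 20, in its classical form, drops a patient seen at 6 months who missed the 3-month visit, and the two-per-arm dropout margin in section 14 was not set for that loss

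*Protocol*

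**What the plan says.** Section 12 makes PES the primary outcome with a 6-month PICOT time frame. The timetable in section 13 schedules PES at 3 and 6 months, and soft tissue contour before surgery and at 3 and 6 months.

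Section 20 states: "Comparisons between two groups and over time will be done by 2-way analysis of variance for repeated measures". Its next sentence sends numeric variables to a t-test or a Mann-Whitney test where the time factor is judged unimportant, without saying how that is judged or for which outcome.

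Section 14 finds that "at least 8 patients were needed for each group with a total number of 16 patients", and then: "This number was increased to 20 patients (10 patients in each group) to compensate for any possible dropouts". The margin is 10 − 8 = 2 patients per arm.

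**The concern.** Classical repeated-measures ANOVA works on complete rows: a patient with one empty visit leaves the whole analysis. PES has two visits, so it falls under this method by default, and so does contour. A patient who skips month 3 but returns at month 6 has the measurement the trial most wants, and the named method does not use it.

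The margin in section 14 is meant for patients who leave the trial. It was not set for patients who stay in it but miss one visit. In a trial of 20, the number analysed could fall below 8 per arm even though 8 or more per arm were seen at 6 months. The analysed group would also consist of those who attended every visit. That is a selected group if attendance is related to healing, although nothing in the protocol shows that it is.

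**Working it through.** **Inputs from the protocol.** Effect size 1.5 (section 14: "effect size was estimated to be 1.5 based on a previous study"), read as a standardised difference because no standard deviation is given; significance level 0.05 (section 20: "A p-value less than or equal to 0.05 will be considered statistically significant"); two-sided ("All tests will be two-tailed"); 1:1 allocation (section 8); 8 needed and 10 enrolled per arm (section 14).

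**Step 1: reproduce section 14.** For a two-sample t-test with n per arm, the noncentrality is 1.5 × √(n/2) on 2n − 2 degrees of freedom. At n = 8 this is 1.5 × √4 = 3.0 on 14 degrees of freedom, and power is 79.7%. That agrees with the stated 80%. Inflating for 20% loss gives 8 / 0.8 = 10 per arm, as stated.

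**Step 2: chance that both arms keep at least 8.** The protocol gives no missed-visit rate. Assume 10% miss the 6-month visit, a share q also misses month 3, and visits are missed independently. A patient is usable with probability p = 0.90 if everyone seen at 6 months counts, and p = 0.90 × (1 − q) if both visits are required. The chance that one arm keeps at least 8 of 10 is the binomial sum over k = 8, 9, 10; squaring it covers both arms.

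| Rule | p | One arm ≥ 8 | Both arms ≥ 8 |
|---|---|---|---|
| Everyone seen at 6 months | 0.900 | 0.930 | about 86% |
| Both visits, q = 5% | 0.855 | 0.833 | about 69% |
| Both visits, q = 10% | 0.810 | 0.708 | about 50% |
| Both visits, q = 20% | 0.720 | 0.438 | about 19% |

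In the first row, for example, 0.1937 + 0.3874 + 0.3487 = 0.9298, and 0.9298² ≈ 0.864.

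If only 5% miss each visit, the chance falls from 0.9885² ≈ 97.7% to 0.934² ≈ 87.2%, a much smaller loss.

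**Step 3: power of the ANOVA itself.** The ANOVA's group effect averages the two PES visits. If the effect is 1.5 standard deviations at both visits and the between-visit correlation is r, the standardised effect on the average is 1.5 / √((1 + r)/2).

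| r | Effect on the average | Power, 8 per arm | Power, 7 per arm |
|---|---|---|---|
| 0.5 | 1.732 | 89.6% | 84.4% |
| 0.7 | 1.627 | 85.6% | 79.8% |
| 0.9 | 1.539 | 81.6% | 75.3% |
| 1.0 | 1.500 | 79.7% | 73.1% |

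The protocol does not give r, so no single power figure can be attached to the ANOVA.

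**The case against.** Four objections deserve an answer.

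- **The exclusion is nowhere written.** It follows from how the classical procedure works, and the handling of gaps may be left to a statistical analysis plan that is not shown. The lack of a missing-data rule is indeed no finding. What stands is that the protocol itself names a method which, as usually run, cannot use a 6-month value without its 3-month partner.
- **Section 20 has another route.** A t-test or Mann-Whitney test at 6 months keeps every patient seen then, so it would be too strong to say that section 20 as a whole deletes such patients. But that route depends on an undefined condition, and nothing ties it to the 6-month PES comparison.
- **The margin may absorb the gaps.** With 10% missing at each visit, the average number of complete rows is 10 × 0.81 = 8.1 per arm, still above 8, and section 13's timetable is backed by a phone call at each follow-up (section 18). This limits the size. The average hides the spread, though: at these rates both arms reach 8 only about half the time.
- **Power.** A reader might infer that losing one further patient per arm takes the planned analysis from 79.7% to 73.1%. Those are t-test powers for a single time point, and a 6-month t-test would not drop the patient. For the ANOVA they apply only at a between-visit correlation of 1.

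A reader might also extend the point to all outcomes. The documents do not support that. Patient satisfaction is listed as binary in section 12, so neither a numeric ANOVA nor a linear mixed model clearly suits it. The section 13 timetable has no 3-month reading for crestal bone level or labial plate thickness. Nor does a calculation with three visits at risk suit PES, which has two; for contour the first reading is preoperative.

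**Conclusion.** The point holds for PES and soft tissue contour. Section 20 fixes a method whose classical form discards observed 6-month data when month 3 is missing, and its alternative route does not reliably prevent this.

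Under the stated assumptions (independent visits, 10% missing at 6 months), the chance of keeping at least 8 in both arms drops from about 86% to about 69%, 50% or 19% as 5%, 10% or 20% also miss month 3. These rates are illustrations, not protocol figures, and with few missed visits the loss is small. The cost in ANOVA power depends on an unstated correlation and is not claimed here.

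A reader might conclude that section 14 is wrong. It is not: 8 per arm reproduces and 10 per arm follows. The change is worth making because it is cheap and keeps primary data, not because the trial is undersized.

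**What to change.** In section 20, analyse the repeated numeric outcomes (PES and contour) with a linear mixed model containing arm, visit and arm-by-visit. Include all randomised patients with at least one post-operative value, use small-sample degrees of freedom, and estimate the arm difference at 6 months from the model.

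At minimum, state that the 6-month PES comparison uses every randomised patient with a 6-month PES, whether or not the 3-month visit was attended.

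Either version takes one or two sentences and needs no extra patients, visits or staff. The small downside of the mixed model is that its degrees of freedom are approximate with about 20 patients; the minimum version avoids this.
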